The primary therapeutic intervention to treat proven NTM lung disease is antibiotic treatment to eliminate the causative pathogen, and thereby to prevent progression of NTM-associated lung destruction and respiratory failure (Daley, 2020). Current American Thoracic Society (ATS), European Respiratory Society (ERS), European Society of Clinical Microbiology and Infectious Diseases (ESCMID), and Infectious Diseases Society of America (IDSA) treatment guidelines for NTM lung disease utilize complex treatment regimens of long duration. Guideline-recommended treatments for treatment-naïve MAC lung disease include a 3-drug regimen administered for a duration of approximately 1.5 years. No standard treatment regimen exists for

treatment-refractory MAC lung disease (Daley, 2020; Haworth, 2017). Patient-centered NTM treatment priorities include the need for improved efficacy (measured by sputum culture conversion) that leads to reducing treatment burden, including a reduction in the duration of treatment; identifying new active drugs with fewer side effects; and eliminating the need for intravenous (IV) administration of drugs (Henkle, 2016).

Epetraborole oral tablets would extend the armamentarium of treatment options available to physicians and offer the potential to decrease the need for potentially toxic or unproven therapies. Epetraborole binds to and inhibits the bacterial leucyl-tRNA synthetase, thereby disrupting protein synthesis and blocking the editing function of this critical bacterial enzyme. A number of in vitro and in vivo studies were conducted to evaluate the antibacterial potential of epetraborole against a variety of mycobacterial species including *M. avium*, *M. intracellulare*, and *M. chimera* (see current Investigator's Brochure).

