- Radiographic response at Month 6 and EOT, defined as overall change from baseline based on blinded central reading of chest CT in the Micro-ITT Population
- By-subject microbiological response (by-subject sputum culture conversion and by-subject microbiological improvement) by epetraborole MIC at Month 6 in the Micro-ITT Population
- Rate of decreased susceptibility among postbaseline MAC isolates, defined as a ≥ 4 -fold increase in epetraborole MIC relative to the baseline isolate MIC, among patients remaining MAC culture-positive at Month 4 or later in the Micro-ITT Population

- Time (in days) to improvement in PRO-based clinical response in the Micro-ITT Population
- Time (in months) to first negative sputum culture and decrease in MAC colony counts by ≥ 1 category in the Micro-ITT Population

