7.5.1.4. Radiographic Assessments (Chest CTs)

Chest CT scans will be evaluated to assess eligibility and pulmonary radiographic response during the study. All chest CTs must be non-contrast and consist of contiguous sections through the lungs, each section of ≤ 3 mm thickness. Low-dose CT scans are acceptable.

Pre-Study chest CTs performed per standard of care may be used to determine eligibility if taken within 6 months of signing the ICF and will serve as the *Screening* chest CT. If the most recent *Pre-Study* chest CT was taken >6 months prior to signing the ICF, a chest CT must be obtained within the Screening Period (*Screening* chest CT).

The interpretation of *Screening* chest CTs (to assess for abnormalities consistent with MAC lung disease, per Inclusion Criterion 3.c) will be performed locally by the site (eg, Investigator or local radiologist). The Investigator is encouraged to review the CT with the local radiologist in cases where cavity size is close to the 5 cm exclusion (see Exclusion Criterion 1).

Radiographic response will be evaluated based on severity, extent of pulmonary disease, and overall improvement between baseline (ie, *Screening* CT scan) and Month 6 and between baseline and EOT. These evaluations and interpretations of digital images of chest CTs will be performed centrally by a member of an independent team of blinded radiologists. A minimum of 8 weeks between 2 chest CT scans is recommended. For example, if EOT occurs before Month 6, the EOT chest CT should be scheduled to occur at least 8 weeks after the *Screening* chest CT. If the last dose of study drug occurs within 8 weeks after the Month 6 chest CT, the EOT chest CT should be scheduled to occur at least 8 weeks after the Month 6 chest CT.

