3.4.1.4 Phase 2 Exploratory Efficacy Endpoints at Month 6 Analysis

In an exploratory analysis, descriptive statistics for clinical response and microbiological response (by-patient sputum culture conversion and by-patient microbiological improvement) at Month 3 (as applicable) and Month 6 will be presented by age category, ALIS use at baseline, presence-absence of any fibrocavitary disease, chest cavity category (non-cavitary, cavity diameter ≤ 3 cm, cavity diameter > 3 cm from EDC), MAC resistance phenotype (ie, macrolide-resistant, amikacin IV-resistant, and amikacin (liposomal, inhaled)-resistant), sex, baseline creatinine clearance category (<60 mL/min, ≥ 60 mL/min to <90 mL/min, or ≥ 90 mL/min), BMI category (<18.5 vs ≥ 18.5 kg/m²), and country of enrollment in the Micro-ITT Population. Forest plots of response by treatment group will be presented across all subsets, but no formal statistical testing will be performed.

Radiographic response at Month 6, defined as overall change from baseline based on blinded central reading of chest CT will be summarized at Month 6 and the proportion of patients meeting the criteria of overall improvement from baseline (Y/N; with Yes defined as those categorized as either “Resolution” or “Improvement”, and No as all other categories or missing interpretation) will be presented by treatment group, along with the treatment difference and associated 95% confidence interval, calculated using the method of Miettinen and Nurminen, including stratification by baseline ALIS use and age (<65 years versus ≥ 65 years) in the Micro-ITT Population.

By-patient sputum culture conversion by Month 6 and by-patient microbiological improvement at Month 3 and Month 6 by epetraborole MIC across all baseline pathogens and within each individual baseline pathogen species will be summarized by treatment group in the Micro-ITT Population. By-pathogen microbiological sputum culture conversion by Month 6 and by-pathogen microbiological improvement at Month 3 and Month 6 will be summarized by treatment group for each individual baseline pathogen in the Micro-ITT Population.

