Radiographic response at Month 6 and at EOT, defined as overall change from baseline based on blinded central reading of chest CT will be summarized at baseline and at Month 6 and at EOT and the proportion of patients meeting the criteria of overall improvement from baseline (Y/N; with Yes defined as those categorized as either "Resolution" or "Improvement", and No as all other categories or missing interpretation) will be presented by treatment group, along with the treatment difference and associated 95% confidence interval, calculated using the method of Miettinen and Nurminen, including stratification by baseline ALIS use and presence or absence of any fibrocavitary disease in the Micro-ITT Population.

Rate of decreased susceptibility among postbaseline MAC isolates, defined as a ≥ 4 -fold increase in epetraborole MIC relative to the baseline isolate MIC at any post-baseline follow-up visit, among patients remaining MAC culture-positive at Month 4 or later will be summarized by treatment group in the Micro-ITT Population. Rates of decreased clarithromycin or IV amikacin susceptibility, defined as a change from interpretation of Susceptible or Intermediate at baseline to Resistant at any post-baseline follow-up visit according to the interpretive criteria provided in Table 1, will be summarized similarly.

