3.5.1 Treatment-emergent Adverse Events (TEAEs)

An AE is defined as any untoward medical occurrence in a clinical investigation patient administered a pharmaceutical product, which does not necessarily have a causal relationship with this treatment. An AE can therefore be any unfavorable and/or unintended sign (including an abnormal laboratory finding), symptom, or disease temporally associated with the use of an investigational medicinal product, whether or not related to the investigational medicinal product (IMP), whether or not related to the IMP. All AEs, including observed or volunteered problems, complaints, or symptoms, are to be recorded on the appropriate eCRF. SAEs occurring from the time of informed consent through LFU will be collected. For non-serious AEs, TEAEs are defined as AEs that started from the time of the first dose of study drug through EOT; for serious AEs, TEAEs are defined as SAEs that started from the time of the first dose of study drug through LFU.

Investigators will monitor each patient for clinical and laboratory evidence for pre-defined AEs of special interest (AESIs) through LFU.

For this study, gastrointestinal intolerance, anemia, and (added prior to the Phase 3 analysis only) pneumonitis are considered AESIs. During the course of the study, additional AESIs may be identified by the Sponsor, and will be documented to support safety analyses at each analysis time point. A list of preferred terms to be included as AESIs by category will be finalized by the Sponsor prior to database lock and unblinding of each planned analysis.

AESIs related to gastrointestinal intolerance include, but are not limited to:

- *C. difficile* colitis

- Pseudomembranous colitis
- *C. difficile* test positive
- Diarrhea
- Nausea
- Vomiting

AESIs related to anemia include, but are not limited to:

- Anemia
- Aplastic anemia
- Coombs negative hemolytic anemia
- Coombs positive hemolytic anemia
- Hematocrit decreased
- Hemoglobin decreased
- Hemolysis
- Hemolytic anemia
- Intravascular hemolysis
- RBC decreased

AESIs related to pneumonitis (for Phase 3 only) included, but are not limited to:

- Pneumonitis
- Hypersensitivity pneumonitis
- Interstitial lung disease
- Pulmonary toxicity

An overview of AEs will be provided including counts and percentages of patients (and event counts) with the following:

- Any TEAEs (overall and by maximum severity)

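### The only between-arm estimate with a confidence interval for the central CT read is improved yes/no, so an effect confined to worsening would leave it unchanged

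*SAP*

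**What the plan says.** Protocol 2.2.2 lists the Phase 3 exploratory endpoint as "Radiographic response at Month 6 and EOT, defined as overall change from baseline based on blinded central reading of chest CT". Protocol 7.5.1.4 describes the assessment more broadly: "Radiographic response will be evaluated based on severity, extent of pulmonary disease, and overall improvement".

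SAP 3.4.3.4 asks for a summary of the read at each of these visits and then dichotomises it. A patient is a Yes if the read is Resolution or Improvement. Everyone else falls under this rule: "and No as all other categories or missing interpretation". The Yes proportion is the quantity compared between arms, and the output is specified in these words: "along with the treatment difference and associated 95% confidence interval, calculated using the method of Miettinen and Nurminen". The two Phase 3 randomisation factors serve as strata, and the population is Micro-ITT. The Phase 2 sections use the same rule (SAP 3.4.1.4, "No as all other categories or missing interpretation", and SAP 3.4.2.2).

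No other part of the SAP compares the arms on the CT read. SAP 3.5 (safety) contains no CT analysis, and SAP 5 lists no change to the radiographic endpoint.

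**The concern.** The endpoint is change, which can go both ways, but the comparison covers only one end of it. Any worsened scan falls in the same cell as an unchanged scan and a scan that was never read. Protocol 1.1 gives the purpose of treating this disease as, in part, "to prevent progression of NTM-associated lung destruction and respiratory failure". It also describes fibrocavitary disease, a Phase 3 stratification factor, as progressing relatively rapidly. Fewer worsened scans is thus a plausible form of benefit, and more worsened scans a plausible form of harm. Neither would have a between-arm estimate with an interval.

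Coding missing reads as No adds a second difficulty. If scans are missing more often in one arm, the yes/no difference moves although the disease does not. The trial was terminated early, so some missing Month 6 scans are plausible, but the documents give no count.

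**Working it through.** **Inputs from the documents.** Planned Phase 3 Micro-ITT size 124 versus 62, 2:1, two-sided 0.05, sized on 30% versus 10% (Protocol 8.2.4.2). The achieved Phase 3 size and the rates of CT improvement, worsening and missing reads are not given. Every CT rate below is an assumption.

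**The plan's own figure.** No power is stated for the radiographic endpoint. For the sizing case (30% versus 10%, 124 versus 62), the normal approximation gives 0.897 and exact enumeration of the unstratified Miettinen-Nurminen score test gives 0.907, against the stated value of approximately 90%. It reproduces, so 124 versus 62 is used for illustration.

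**1. Improvement equal, worsening different.** Take 25% improved in both arms. The planned difference is 25 − 25 = 0 points, and its interval excludes zero about 5% of the time whatever happens to worsening. The difference in the proportion worsened is d = p1 − p0, with approximate interval d ± 1.96 × √[p1(1 − p1)/n1 + p0(1 − p0)/n0]. For 15% (epetraborole) versus 30% (placebo): √(0.15 × 0.85/124 + 0.30 × 0.70/62) = 0.0664, so −15 ± 13 points. Power is from the exact score test.

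| Worsened, epetraborole vs placebo | Difference, points (95% CI), 124 vs 62 | Power, 124 vs 62 | Power, 62 vs 31 |
|---|---|---|---|
| 15% vs 30% | −15 (−28 to −2) | 67% | 41% |
| 10% vs 30% | −20 (−33 to −7) | 92% | 67% |
| 10% vs 20% | −10 (−21 to +1) | 47% | 26% |
| 30% vs 15% (harm) | +15 (+3 to +27) | 63% | 34% |

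The last column assumes that termination halved the sample.

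**2. Both ends of the scale move.** Assume four ordered categories (resolution / improved / unchanged / worse), with 40,000 unstratified simulations per case and no missing reads. The tests are the Miettinen-Nurminen score test for each proportion and a tie-corrected Wilcoxon test for the ordered scale.

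- *Mainly less worsening*, 2/20/66/12% versus 0/15/58/27%: yes/no 20%, ordinal 66%, proportion worsened 71%. At an assumed 70 versus 35: 12%, 43% and 50%.
- *Common odds ratio of 2*, placebo 0/15/60/25%. The improved odds go from 0.15/0.85 = 0.176 to 0.353, that is 26%. The not-worse odds go from 3 to 6, that is 86%, so 14% worsened. Yes/no 41%, ordinal 60%. At 70 versus 35: 24% and 38%.
- *No effect*: all tests about 5%.
- *Effect confined to improvement*: the order reverses (63% for yes/no against 50% ordinal in one assumed case).

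The SAP plans no p-value for this row. Power here stands for how often an estimate would be distinguishable from zero.

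**3. Missing coded as No.** With true improvement 25% in both arms and 10% missing on placebo, the observed difference is 0.25 × (1 − m) − 0.25 × (1 − 0.10). For m = 20% on epetraborole it is −2.5 points, and for m = 30% it is −5 points, with no true effect.

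**The case against.** The best defence is that the information is not lost. SAP 3.4.3.4 says that overall change is summarised as well as dichotomised, and SAP 3.1.3 summarises categorical data with counts and percentages. If that table is by arm, a reader can subtract. A reader might infer from the yes/no rule that worsening goes unreported; the text does not support that. What is missing is a planned treatment difference with an interval, and an explicit statement that the table is by arm.

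Other parts of the defence also stand:

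- The stated objective is radiographic response, and progression is not a named radiographic endpoint. It would go too far to say that the objective is left unanswered.
- Only Resolution and Improvement are named. That the other categories include unchanged and worse is a reasonable inference, and whether they form a clean order is unknown. The ordinal analysis must be conditional on that.
- Protocol 1.1 says that nodular bronchiectatic disease, the most common form, can progress very slowly. Worsening by Month 6 may be rarer than assumed here, which would shrink the gains.
- SAP 3.5.1 records that "added prior to the Phase 3 analysis only) pneumonitis are considered AESIs", and a reader might treat CT worsening as the blinded signal for it. Nothing in the documents says that the central read separates pneumonitis from MAC progression, and pneumonitis is already summarised as an adverse event category.
- Restricting to patients with a read conditions on a post-randomisation event.
- At EOT the scan time depends on response. Under Protocol 3.1.1 non-converters reach EOT at Month 6 and converters continue to as late as Month 16; the scan-spacing advice in Protocol 7.5.1.4 can shift the non-converters' scan by about 8 weeks. An EOT comparison of worsening would mix outcome with follow-up time.

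None of this supplies an interval for worsening at Month 6.

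**Conclusion.** The point holds in a limited form. For the central CT read, improved yes/no is the only quantity with a planned treatment difference and interval. An effect confined to worsening, benefit or harm, would leave that estimate at zero. In the assumed cases the yes/no row detects such an effect about 5% of the time, against 47% to 92% for a direct comparison of worsening at 124 versus 62 and 26% to 67% at half that size. The structural conclusion needs only that worsening is among the read categories. The percentages rest on assumed rates, an assumed sample size, no stratification and complete reads, so they illustrate and do not predict.

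The endpoint is exploratory and outside the testing hierarchy. This is a gap in estimation, not a type I error problem, and a minor one.

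**What to change.** Before Phase 3 unblinding, amend SAP 3.4.3.4 as follows:

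1. Keep the improvement yes/no row as planned.
2. State the read categories, and show the full distribution by arm at Month 6 and EOT with missing reads as a separate row.
3. At Month 6, among patients with a read, add the Miettinen-Nurminen difference and 95% confidence interval for the proportion worsened, stratified by ALIS use and fibrocavitary disease. If the categories are ordered, add a stratified ordinal comparison (van Elteren or proportional odds).
4. Add a simple sensitivity analysis for missing reads, for example counting them all as worsened and then all as not worsened.
5. At EOT, report the same items descriptively only, and say that scan timing depends on conversion status.
6. Do not present the read as a measure of pneumonitis.

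The cost is a few lines of SAP text and code, with no new scans or readers. The downside is one or two more exploratory estimates, with the ordinal one less sensitive than yes/no if the effect is confined to improvement. After unblinding, SAP 1 would make the same analysis a documented post hoc deviation, which would carry less weight.

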3.5 Safety Analysis

Safety data will be summarized by actual treatment received (and in total for selected analyses) as a primary endpoint in Phase 2 and a secondary endpoint in Phase 3 based on the Safety Population. All the analyses in this section will be run on the Safety Population of each study phase, and will be generated separately for all safety data collected through the Month 6 visit and again for all safety data collected through the end of study in Phase 2, while a single analysis of safety through the end of study will be generated for Phase 3. Safety data across the Phase 2 and 3 Safety populations will not be pooled as part of this analysis plan. No hypothesis testing will be performed; all analyses will be descriptive in nature.

Assessments of safety will include the following:

- Assessment of TEAEs;
- Changes from baseline and in laboratory tests (including chemistry, hematology, and urinalysis parameters), including shifts in severity grade or relative to normal ranges for selected laboratory parameters;
- Changes from baseline in vital signs; and
- Change from baseline in 12-lead ECG parameters.

